## 2.1. Analysis Periods/Phases

Because the analysis of adverse events (AEs) will be presented per period (and not per time point), these will be assigned to the analysis periods based on [Table 3](#).

For the analysis that will be presented by time point (eg, immunogenicity data), the electronic case report form (eCRF) visit schedules will be used for the post baseline assessments as follows:

- For the analysis based on the per protocol set, only assessments that fall within the protocol-defined visit window will be used.
- For other analyses based on the full analysis set (if applicable), the assessments that fall outside the protocol-defined windows will also be included. If only unscheduled visits are present for a time point, then the one closest to the scheduled visit will be used. If distances of multiple assessments to the scheduled visit are equal, the measurement with the latest date will be used.

**Table 3: Analysis Period Definitions**

Phase	Period	Interval	
		From	To
Screening		Date and time of signing the informed consent form	One minute prior to start of post-dose 1 period
Regimen	Post-dose 1	Date and time of first vaccination	Minimum of: 
 
a) 23:59 on the date of last contact (for early discontinuation)
 
b) 23:59 on the date of database cut-off date in case of primary (or interim) analysis
 
c) 23:59 of 28 days after the first vaccination (23:59 of day of vaccination + 28 days)
 
d) One minute prior to post-dose 2 period
 

Phase	Period	Interval	
		From	To
Post-dose 1 FU		One minute after post-dose 1 period ends	Minimum of: a) 23:59 on the date of last contact (for early discontinuation) b) 23:59 on the date of database cut-off date in case of primary (or interim) analysis c) One minute prior to post-dose 2 period
Regimen	Post-dose 2	Date and time of second vaccination	Minimum of: a) 23:59 on the date of last contact (for early discontinuation) b) 23:59 on the date of database cut-off in case of primary (or interim) analysis c) 23:59 of 28 days after the second vaccination (23:59 of day of vaccination + 28 days)
Post-dose 2 FU		One minute after post-dose 2 period ends	Minimum of: a) 23:59 on the date of last contact (for early discontinuation) b) 23:59 on the date of database cut-off in case of primary (or interim) analysis c) 23:59 on the date of last study visit d) One minute prior to post-dose 3 period
Regimen	Post-dose 3	Date and time of third vaccination	Minimum of: a) 23:59 on the date of last contact (for early discontinuation) b) 23:59 on the date of database cut-off in case of interim analysis c) 23:59 of 28 days after the third vaccination (23:59 of day of vaccination + 28 days)
Post-dose 3 FU		One minute after post-dose 3 period ends	Minimum of: a) 23:59 on the date of last contact (for early discontinuation) b) 23:59 on the date of database cut-off in case of primary (or interim) analysis c) 23:59 on the date of last study visit

FU: Follow-up

Note: Dose 3 corresponds to booster vaccination.

## 2.2. Pooling Algorithm for Analysis Centers

There is more than 1 site in this study and data from the different sites will be pooled for analysis.

## 2.3. Analysis Sets

Vaccination assignment will follow the “as treated” principle. That is, participants will be analyzed according to the actual vaccine received.

### 2.3.1. Full Analysis Set

The full analysis set will include all participants with at least one study vaccine administration documented.

### 2.3.2. Per Protocol Analysis Set

The per protocol analysis set for the main part of the study (Groups 1-4) will include all randomized and vaccinated participants, who received both Dose 1 and Dose 2 vaccinations (administered within the protocol-defined window), had at least one postvaccination (ie, after the date of vaccination) evaluable immunogenicity sample, and had no major protocol deviations that may influence the immune response. Similarly, the per protocol analysis set for the Booster Cohort (Groups 5-6) will include all vaccinated participants, who received Dose 1, Dose 2, and the booster vaccination (ie, both Dose 2 and booster vaccination within the protocol-defined window), had at least one postvaccination (ie, after the date of vaccination) evaluable immunogenicity sample, and had no major protocol deviations that may influence the immune response.

Note that the per protocol analysis set will only be defined for participants included in the immunogenicity subset and the booster cohort. The following will be considered for the immunogenicity analysis based on the per protocol analysis set:

- The primary and secondary hypotheses will be based on those in the set with data at 21 days post Dose 2 and 56 days post Dose 1, respectively. Participants who will receive incorrect batch (other than the one randomized to) of vaccination will only be excluded from these hypothesis tests.
- Immunogenicity samples obtained after missed doses (or out-of-window Dose 2 or Dose 3 vaccinations), samples obtained after natural infection (if applicable), or samples obtained outside the protocol-defined window will be excluded in graphs and tables showing descriptive statistics. These measurements will however be shown in listings, together with the indication that they are not used in the analysis.
- If more than 10% of participants from the full analysis set are excluded from the per protocol analysis set, then the immunogenicity analysis (including both primary and secondary hypothesis testing) will be repeated on the full analysis set to evaluate the robustness of the analysis results.
- The upper limit of the window around Day 57 (Dose 2) was extended to Day 85 (ie, Day 57+28 days) in the main part of the study (Groups 1-4) in order to reduce the number of additional participants needed for the primary and secondary immunogenicity analyses. Therefore, both the primary and secondary objectives (based on data of only participants in the per protocol analysis set who received the second vaccination within the original window [ $\pm 3$  days] around the Day 57 visit) will be assessed as sensitivity analyses (albeit with reduced power for testing the hypotheses).

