6.2. Contraindications to Second Vaccination

A participant will not be given the Dose 2 or booster dose vaccination if he or she experiences any of the following events at any time after the Dose 1 vaccination:

1. Anaphylaxis clearly attributable to vaccination with study vaccine; *OR*
2. Generalized urticaria within 72 hours of vaccination considered to be related to study vaccine; *OR*
3. A serious adverse event considered to be related to study vaccine; *OR*
4. Injection site ulceration, abscess, or necrosis considered to be related to study vaccine; *OR*
5. Any other safety concern threatening the participant's safety.

Participants experiencing any of the events described above must not receive any further study vaccine but should continue be monitored for safety and for immunogenicity according to the protocol if this does not result in safety risks for the participant.

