### **Alternative Hypothesis**

Three consecutive lots of Ad26.ZEBOV (Lots A, B, and C) as Dose 1 paired sequentially in 3 groups with 3 consecutive lots of MVA-BN-Filo (Lots 1, 2, and 3) as Dose 2 induce equivalent GMCs of the EBOV GP-specific antibody concentrations 21 days post Dose 2, for all 3 pairwise comparisons (ie, Groups 1 versus [vs] 2, 1 vs 3, and 2 vs 3 [see overview of the groups in [Table 2](#)]).

Equivalence of any 2 groups (Ad26.ZEBOV as Dose 1 followed by MVA-BN-Filo as Dose 2) will be shown if the 95% confidence interval (CI) of the estimated GMC ratio lies entirely within 0.5 and 2.0. These equivalence limits were chosen primarily based on the population variability as measured by the ELISA assay and are expected to be adequate to detect potential clinically meaningful differences in GMCs. Immunogenic equivalence of the 3 different lots of Ad26.ZEBOV (Lots A, B, and C) paired sequentially in 3 groups with 3 different lots of MVA-BN-Filo (Lots 1, 2, and 3) will be established if equivalence is shown for all 3 pairwise comparisons.

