## **1.4. Sample Size Justification**

The following assumptions were used in the sample size determination:

- A standard deviation of 0.55 on the  $\log_{10}$  scale (binding antibody levels against the EBOV GP using ELISA [EU/mL] 21 days post Dose 2 vaccination, following Dose 1 on Day 1 and Dose 2 on Day 57). This standard deviation was obtained by adding 10% to the maximum observed standard deviation at 56 days post Dose 1 vaccination in the Phase 2/3 studies and will also ensure adequate power in demonstrating lot-to-lot consistency at 56 days post Dose 1 vaccination (ie, secondary objective).
- An overall 5% dropout rate.

In addition, specific assumptions were made for the equivalence testing for the primary and secondary objective:

Assumptions specific to equivalence testing:

- A relative difference of 10% in GMC of binding antibodies between groups (ie, Groups 1 to 3). This is expressed as  $GMC_{(1)} = 0.9 \times GMC_{(3)}$ , where  $GMC_{(1)}$ ,  $GMC_{(2)}$ , and  $GMC_{(3)}$  denote the ordered GMCs. This relative difference is based on both the process variability in vp content of the Ad26.ZEBOV lots and Inf U content of the MVA-BN-Filo lots. A linear relationship between  $\log_{10}$ -transformed vaccine contents (ie, Ad26.ZEBOV and MVA-BN-Filo) and  $\log_{10}$ -transformed GMC of binding antibodies (ELISA GMC) was assumed.
- Clinical equivalence limits on the GMC ratio are 0.5 and 2.0.

Under the above assumptions, a total of 144 participants per group receiving Ad26.ZEBOV as Dose 1 and MVA-BN-Filo as Dose 2 would yield an overall power of at least 90% to show immunogenic equivalence of the 3 groups (Groups 1 to 3) 21 days post Dose 2 vaccination (ie, with 96.55% power for each of the 3 pairwise comparisons [ie, Groups 1 vs 2, 1 vs 3, and 2 vs 3]). PASS 11 was used for the sample size calculation. In order to enlarge the safety database, the total number per group was increased to 234 (ie, additional 90 participants per group for safety only).

A randomization ratio of 6:6:6:1 (Group 1:Group 2:Group 3:Group 4) yields an overall sample size of 741 participants, with 234 participants per group (in Groups 1 to 3) receiving Ad26.ZEBOV and MVA-BN-Filo, and 39 participants receiving placebo (Group 4). In addition, approximately 60 participants will be randomized in a 5:1 active:placebo ratio (Group 5:Group 6), to provide a reasonable estimation of the humoral immune response to a booster dose.

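### The Ad26.ZEBOV lot test at 56 days post Dose 1 drops participants with a valid pre-Dose 2 sample because of what then happens with Dose 2

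*SAP*

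**What the plan says.** SAP 2.3.2 defines a single per protocol set for Groups 1-4, repeated from Protocol 11.1. It takes randomized and vaccinated participants "who received both Dose 1 and Dose 2 vaccinations (administered within the protocol-defined window"), with at least one evaluable postvaccination sample and no major deviation that may influence the immune response. Both confirmatory hypotheses are tested within that set: the primary in members with data 21 days post Dose 2, the secondary in members with data 56 days post Dose 1. SAP 6.3.1 confirms that the secondary objective is assessed in the same way as the primary, which uses the per protocol set only.

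A further rule acts on the two tests and not on the set: "Participants who will receive incorrect batch (other than the one randomized to) of vaccination will only be excluded from these hypothesis tests". It does not say which dose the wrong batch must concern.

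The secondary endpoint is measured before Dose 2. Protocol 3.1 lists the Day 57 sample as pre Dose 2, and the Time and Events Schedule places that blood draw before vaccination.

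Protocol 6.2 lists reasons to withhold the next dose: "A participant will not be given the Dose 2 or booster dose vaccination if he or she experiences any of the following events". They include related serious adverse events and generalized urticaria. Protocol 6.2 and 10.2 keep such participants under immunogenicity follow-up where this is safe, so a Day 57 sample is expected from them.

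**The concern.** The secondary test asks whether three Ad26.ZEBOV lots give equivalent responses before MVA-BN-Filo is given. A missing, late or wrong-batch Dose 2 cannot change a concentration in blood already drawn, yet each removes the participant from this test.

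Two things are at stake. The first is the comparison itself. The Dose 1 lots are compared among people selected partly by their Dose 2 experience. Some grounds for withholding Dose 2 are reactions to Dose 1, so the selection could depend on the lot being tested. The second is the loss of evaluable samples in a trial where the sponsor widened the Dose 2 window to limit exclusions.

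The section is also not consistent with itself. Its sample-level rule for descriptive tables and graphs removes samples taken after a missed or out-of-window dose. That logic would keep the pre-Dose 2 sample, whereas the participant-level rule discards it from the test.

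**Working it through.** **Which samples are at issue.** The pre-Dose 2 sample is taken at the Dose 2 visit, which limits what can be recovered.

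| Situation | Valid Day 57 sample? | In the secondary test now? |
|---|---|---|
| Does not attend the Day 57 visit | No | No |
| First seen after Day 85 | No; outside the visit window (SAP 2.1) | No |
| Bled in window, Dose 2 withheld or refused | Yes | No |
| Bled in window, Dose 2 postponed past Day 85 | Yes | No |
| Bled in window, wrong MVA-BN-Filo batch | Yes | No |
| Bled in window, relevant major deviation only afterwards | Yes | No |

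Only the last four rows are lost for a reason unrelated to the Dose 1 measurement.

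**Inputs.** From SAP 1.3 and 1.4:
- Decision rule: equivalence of a pair "will be shown if the 95% confidence interval (CI) of the estimated GMC ratio lies entirely within 0.5 and 2.0"; all three pairs must pass.
- Margin: "Clinical equivalence limits on the GMC ratio are 0.5 and 2.0", so m = log10(2) = 0.3010.
- True difference: "A relative difference of 10% in GMC of binding antibodies between groups (ie, Groups 1 to 3"), so d = -log10(0.9) = 0.0458.
- Variability: "A standard deviation of 0.55 on the" log10 scale. The SAP says this choice "will also ensure adequate power in demonstrating lot-to-lot consistency at 56 days post Dose 1 vaccination", so it applies to the secondary test.
- 144 per group with 5% dropout: 144 x 0.95 = 136.8, taken as 137.

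**The plan's figure.** With SE = 0.55 x sqrt(2/n), the normal approximation for one pair is

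power = Φ((m - d)/SE - 1.96) + Φ((m + d)/SE - 1.96) - 1.

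At n = 137, SE = 0.0665. The terms are Φ(3.84 - 1.96) = 0.970 and Φ(5.22 - 1.96) = 0.999, giving 96.95%. The exact t version gives 96.85%. The plan states 96.55%, which is 0.90^(1/3); 0.9655^3 = 90.0%. The plan's figure is reproduced.

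**Power by loss.** The documents do not give the number of valid samples lost, so the loss is an assumption. Pairwise power is exact t. Joint power is simulated (400,000 runs), with the middle lot either halfway between the extremes or equal to one of them.

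| Loss per group | n | Per pair | Joint, halfway | Joint, at an extreme |
|---|---|---|---|---|
| 0% | 144 | 97.49% | 95.88% | 94.98% |
| 2% | 141 | 97.23% | 95.27% | 94.46% |
| 5% | 137 | 96.85% | 94.61% | 93.70% |
| 10% | 130 | 96.05% | 93.17% | 92.12% |
| 15% | 122 | 94.90% | 91.10% | 89.79% |

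With the middle lot halfway, recovering a 2% loss adds 95.88 - 95.27 = 0.61 points of joint power, and recovering 5% adds 95.88 - 94.61 = 1.27. From a lower base, going from 130 to 137 adds 1.44 points (1.58 with the middle lot at an extreme).

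**Possible selection effect.** If a fraction q is dropped from one lot only, and its mean log10 concentration differs by δ from those kept, that lot's GMC shifts by a factor 10^(qδ). With δ = 0.3 (about twofold), q = 2% gives 1.014 and q = 5% gives 1.035. Both q and δ are illustrative. These shifts are small against limits of 0.5 and 2.0.

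**The case against.** The strongest reply is that little is at stake and a safeguard exists. SAP 2.3.2 repeats the immunogenicity analysis, including both hypothesis tests, on the full analysis set if more than 10% are excluded from the per protocol set, and the full analysis set has no Dose 2 condition. This stands as a partial answer. The repeat is a robustness check and not the confirmatory test, and it admits out-of-window samples (SAP 2.1). Its trigger is also unclear. Counted over all participants, the 285 safety-only participants alone make 285/741 = 38%; counted within the immunogenicity subset, exclusions must pass 10% of 456, that is 45.6. The ±3-day sensitivity analysis does not help, because it also conditions on Dose 2 timing.

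A single set for both tests is a legitimate preference, because it keeps the Dose 1 and regimen results in largely the same people.

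Three stronger readings are tempting, and the documents do not support them.
- A reader might take the 22% who did not return within ±3 days as valid samples lost, leaving about 144 x 0.78 = 112 per group. That figure belongs to the superseded window. No-shows have no sample, those first seen after Day 85 have none in window, and the protocol allows additional recruitment.
- A reader might infer that all these exclusions stem from events after the endpoint. Most of the Protocol 6.2 and 10.2 reasons (urticaria, related serious event, pregnancy, code break) would normally precede the Day 57 draw; only the omission of Dose 2 follows it. It is therefore not established that every such event leaves the Dose 1 response unaffected.
- A reader might take correct batch as a condition of the per protocol set. It is a separate exclusion from the two tests.

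**Conclusion.** The point holds as a mismatch between the secondary endpoint and the population in which it is tested. A stated rule removes valid Dose 1 samples for Dose 2 reasons, and the wrong-batch rule does the same for a wrong Dose 2 batch.

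The size is small. If 2-5% of 144 per group were recovered, joint power would rise by about 0.6-1.3 points from a level already above 90%. This rests on the plan's SD of 0.55 and 10% difference, and on an assumed number of affected participants. The rule could select on a consequence of the lot, but the documents give no evidence of a difference between lots, so a reader should not infer that the Dose 1 comparison is biased. This is a cheap improvement and not a threat to the secondary conclusion.

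**What to change.** In SAP 2.3.2, define a separate population for the secondary hypothesis:
- correct Ad26.ZEBOV batch at Dose 1;
- an evaluable pre-Dose 2 sample within the Day 57 visit window (Day 54-85), since the schedule gives no separate sampling window;
- no major deviation before that sample that may influence the response.

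Apply the Dose 2 timing and MVA-BN-Filo batch conditions to the primary hypothesis only. Record this in SAP 1.6 as a change from Protocol 11.1. Events before the draw that may influence the response remain covered by the third condition where they count as major deviations.

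The cost is a few sentences and one population flag, with no new data. The downside is that the primary and secondary tests would use slightly different participants, which the report should state with the counts by group.

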Depending on the extent of the COVID-19 impact on the study, additional participants will be recruited in the immunogenicity subset. For instance, shortly after participants received Dose 1 vaccination, “stay-at-home” orders were imposed in the areas where the sites were located. Although the sites had implemented appropriate safety measures to prevent spread of SARS-CoV-2, approximately 22% of participants did not return to the site within the original protocol-defined windows ( $\pm 3$  days) for Dose 2 administration. Investigators were then instructed to bring participants back to the site to complete the vaccine regimen, even if they were out of window. Currently, the “stay-at-home” orders have been lifted and some

participants are returning to the sites for follow-up. In order to reduce the number of additional participants needed for the primary and secondary immunogenicity analyses without jeopardizing the evaluation of the primary and secondary objectives of the study, the window around Dose 2 administration for the main part of the study (Groups 1-4) was widened in CTP Amendment 3. In particular, the upper limit of the window around Day 57 (Dose 2) was extended to Day 85 (ie, Day 57+28 days). The widening of window was deemed acceptable after examination of the immunogenicity data from previous studies (ie, VAC52150EBL2001 and VAC52150EBL2002) in which Dose 2 was administered at intervals  $\geq$ 56 days. Although there appears to be a trend of increasing GMCs with increasing intervals between Dose 1 and Dose 2 from those studies, the variability (standard deviation) of the immune responses (binding antibody levels against the EBOV GP using ELISA [EU/mL]) remains stable and in line with the currently assumed standard deviation of 0.55 (on the log10-scale). Assuming that the delayed Dose 2 administration will be randomly distributed among the groups (ie, Groups 1-4), widening the acceptable time frame to administer Dose 2 by increasing the upper limit of the window to 28 days (ie, Day 57+28 days) is not expected to adversely affect the primary and secondary objectives of the study. See CTP Amendment 3 for further details. Unless otherwise mentioned in this document, the “protocol-defined window” refers to the visit windows as defined in CTP Amendment 3.

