### **1.6. Changes to Planned Analyses**

- In the main part of the study (Groups 1-4), a planned total number of at least 741 participants were to be enrolled with the first 456 participants (144 in each of Groups 1 to 3 and 24 in Group 4) to be included in the immunogenicity subset and the remaining 285 for safety only (see CTP Sections 3.1 and 11.2 for details). Due to operational feasibility, the first 57 out 93 participants from each of 8 study sites were to be included in the immunogenicity subset. Protracted contract negotiations for 1 site resulted in the inability of the site to participate in the study. Therefore, it was decided to redistribute the allotment of the 93 participants to the sites that nearly completed enrollment for their original allotment and 57 of these were to be included in the immunogenicity subset. However, there was an oversight and immunogenicity subset slots were not opened in IWRS resulting in all remaining 93 participants being randomized in the safety only cohort. Therefore, there was no baseline immunogenicity sample obtained for any of these participants. In order to ensure that 456 participants are part of the immunogenicity subset and to limit the potential imbalance in the number of participants in each group for the primary and secondary hypothesis testing, the last 57 participants in the main study who were initially for safety only will be included in the immunogenicity subset.
- A full physical examination is only conducted at screening and any abnormality is recorded on the medical history form of the eCRF. At other visits, only abbreviated, symptom-directed examinations are performed per the investigator's discretion and the clinically significant abnormal findings are recorded as AEs. Accordingly, physical examination findings will only be included in the analysis of medical history and AEs.

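### Does the 10% rule for repeating the immunogenicity analysis on the full analysis set need its denominator named?

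*SAP*

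**What the plan says.** SAP 2.3.1 defines the wider population: "The full analysis set will include all participants with at least one study vaccine administration documented". It is not limited to those bled for immunogenicity. SAP 2.3.2 then notes that "the per protocol analysis set will only be defined for participants included in the immunogenicity subset and the booster cohort". Among the points listed under that note is the trigger: "If more than 10% of participants from the full analysis set are excluded from the per protocol analysis set", the immunogenicity analysis, with both hypothesis tests, is run again on the full analysis set as a check on robustness.

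SAP 1.6 divides the planned 741 participants of Groups 1-4 into an immunogenicity subset of 456 and "the remaining 285 for safety only". The sample size in SAP 1.4 assumes "An overall 5% dropout rate". SAP 1.2 now expects a higher rate and reports that "approximately 22% of participants did not return to the site within the original protocol-defined windows" for Dose 2. SAP 6.3.1 assesses the primary objective in the per protocol set only. The protocol's sections on analysis sets (11.1) and immunogenicity analyses (11.3) contain no such trigger.

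**The concern.** The rule compares two sets that were never meant to cover the same people. If its base is everyone vaccinated, the safety-only participants count as excluded before a single visit is missed, and a rule written as a condition can never be false. If exclusion means removal from among those eligible, the rule becomes a real condition. No sentence says which is meant. SAP 2.4 has two other 10% rules and names the base of each, so the omission here cannot be put down to house style.

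At stake is whether any supportive test of the two equivalence hypotheses includes people dropped from the per protocol set. The ±3-day sensitivity analysis does not, since it is "based on data of only participants in the per protocol analysis set who received the second vaccination within the original window". The delayed-Dose-2 outputs of SAP 2.4 and 6.3.1 require more than 10% of the subset to be dosed outside the widened window. Everyone so dosed is a per protocol exclusion, so those outputs cannot appear while total exclusions are at or below 10%. With few exclusions, then, one reading of the trigger gives a robustness test and the other gives none.

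**Working it through.** **Design counts** (SAP 1.2 and 1.4). Subset: 3 × 144 + 24 = 456. Groups 1-4: 3 × 234 + 39 = 741. Safety only: 741 − 456 = 285, which agrees with SAP 1.6.

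**Literal reading.** Excluded by design: 285/741 = 38.5%. The full analysis set also covers the booster cohort of 60, so study-wide the figure is 285/(741 + 60) = 285/801 = 35.6%. Both exceed 10% with no dropout at all, so the repeat always runs.

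**Contextual reading.** Base 456: 10% is 45.6. Since 45/456 = 9.9% and 46/456 = 10.1%, the rule is met from 46 exclusions. The cut-off depends on who is counted:

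| Base | 10% of base | Met from |
|---|---|---|
| Groups 1-4 subset, 456 | 45.6 | 46 (10.1%) |
| Three lot groups, 3 × 144 = 432 | 43.2 | 44 (10.2%) |
| Subset plus booster cohort, 456 + 60 = 516 | 51.6 | 52 (10.1%) |

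A hybrid is also possible: base 741, counting only eligible people as excluded. It needs 75 exclusions (10% of 741 = 74.1), which is 75/456 = 16.4% of the subset. Extra recruitment into the subset would move all of these.

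**Where the two main readings part.** They disagree for 0 to 45 exclusions of 456 and agree from 46.

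- At the 5% planning rate: 0.05 × 456 = 22.8, about 23. Contextual 23/456 = 5.0%, no repeat. Literal (285 + 23)/741 = 308/741 = 41.6%, repeat.
- At 22%, assuming everyone who missed the ±3-day window stayed excluded and was spread evenly: 0.22 × 456 = 100.3, about 100. Contextual 100/456 = 21.9%. Literal (285 + 100)/741 = 385/741 = 52.0%. Both repeat.

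Neither is a forecast. The 5% is dropout, whereas per protocol exclusion also covers Dose 2 timing, lack of an evaluable sample and major deviations. The 22% refers to a window since widened to −3/+28 days and counts only Dose 2 timing, so it does not bound total exclusions in either direction.

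**What the repeat would contain.** The protocol's Time and Events Schedule limits blood sampling for immunogenicity to the subset and Groups 5-6. The safety-only participants have no scheduled result to contribute. The data in the repeat are therefore those of vaccinated subset participants with a sample (and the booster cohort for its own outputs), whichever reading set it off.

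**The case for a change.** The strongest case for acting is that the ambiguity can be shown on the page, the correction is one phrase, and the readings conflict at the dropout rate the sample size assumes. Because SAP 2.4 specifies its bases, a reader is not free to insert the subset into SAP 2.3.2. A robustness check should not depend on an interpretation chosen after unblinding.

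Much of this stands. The denominator is not named, and with 45 or fewer exclusions the repeat is the only planned test of either hypothesis that would bring excluded participants back.

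Three things limit its force. First, context favours one reading: the trigger sits directly below the note confining the per protocol set to the subset and booster cohort, and a person for whom a set is undefined is not naturally excluded from it. Second, the 5% scenario is no longer what the plan expects, because SAP 1.2 now anticipates more. Third, excluded participants do not vanish from the report. They stay in the full-analysis-set tables: baseline characteristics, including baseline antibody positivity for the subset (SAP 4.1), Dose 2 timing (4.3) and safety (5). Major deviations are summarised as well (4.4). The SAP 2.3.2 sentence "These measurements will however be shown in listings, together with the indication that they are not used in the analysis" concerns particular samples, such as those taken after a missed or mistimed dose. It does not consign whole participants to listings.

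**Conclusion.** The gap is real but no change to the plan follows. Followed literally, the plan always produces a supportive repeat, which is harmless and slightly more informative. Followed in context, it produces the repeat once exclusions pass 10% of those eligible, which is an ordinary tolerance for a robustness check. A sensible analyst would take the base to be vaccinated immunogenicity-subset participants in Groups 1-4, with the booster cohort looked at separately, and could equally run the repeat regardless.

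The effect is confined to whether one supportive analysis appears, and only if exclusions stay at or below 45 of 456 (9.9%). The primary per protocol test, the all-three-pairs equivalence decision and the data in any repeat are the same on both readings. This rests on the planned counts of 456 and 741, on safety-only participants having no immunogenicity samples, and on an exclusion rate under the widened window that the documents do not give. The wording could be tidied at any later revision, but nothing in the trial's conclusions depends on it.
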